- History of previous psychiatric disorders, special attention to depression, previous suicidal attempts and other substance use disorders
- Previous and current medical conditions.
- History of alcohol dependence: familial cases of alcohol dependence, age of onset, mode(s) of alcoholisation, list of alcohol-use, CNS and somatic disorders, liver function tests, previous attempts of detoxification, alcohol consumption during the last month prior to inclusion. History of delirium tremens or abstinence-induced seizures
- Seizures, life time, alcohol-induced and non-alcohol-induced (see medical concerns section 1.3)
- Previous and current medication

Physical examination

A general physical examination including weight, examination of throat, armpits (lymph nodes), examination of mouth and throat, auscultation of heart and lungs, and palpitation of abdomen will be performed at the time points indicated above. Attention will be paid to abnormalities, which may have a bearing on the conduct of the trial (e.g., hypertension).

Vital Signs

The vital signs taken are blood pressure (systolic and diastolic) and heart rate and will be measured after 10 minutes of rest. The weight will be measured in kilograms with the patient lightly clothed but without shoes.

Clinical Laboratory parameters

Phosphatidylethanol in blood (B-PEth)

The direct alcohol marker PEth is found in red blood cells in humans in the presence of alcohol (Varga et al., 2000). The sensitivity of PEth is 94.5% and the specificity 100% (Hartmann et al., 2007), which is higher than for the commonly used alcohol markers CDT and GGT (Aradottir et al., 2006; Stewart et al., 2010; Hahn et al., 2012). The half-life of PEth is approx. one week, and the detection window days to several weeks (Wurst et al., 2010; Gnann et al., 2012; Hill-Kapturczak et al., 2018). There is no gender difference (Stewart et al., 2009) and liver disease has no influence on PEth levels (Stewart et al., 2009; Stewart et al., 2014). The positive correlation between PEth and alcohol intake has been established (Gnann et al., 2012; Stewart et al., 2014; Kechagias et al., 2015). PEth as a primary variable is shown to be superior to alcohol markers CDT and GGT (Walther et al., 2015) as well as self-reported alcohol intake (de Bejczy et al., 2015).

Carbohydrate-deficient transferrin (CDT)

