8.2. Statistical analysis

The main hypotheses that will be tested in a hierachial fashion are:

- Combined treatment with VAR and BUP reduces blood concentrations of B-PEth from baseline and significantly more than double-placebo, VAR or BUP alone.
- VAR reduces B-PEth from baseline and significantly more than double-placebo.

The ANCOVA analysis will compare the mean values of the variable in question for the different treatment groups hierachially. Regulatory agency will consider only one specific primary objective and since the two primary endpoints fulfill regulatory requests independently and separately, no adjustment for multiplicity has been done. As testing between treatments are performed in a hierachial fashion, no adjustment for multiple testing has been done.

The SAS® software, version 9.2 or higher, will be used to produce all of the statistical outputs.

All efficacy and safety variables will be presented using descriptive statistics and graphs as appropriate.

Safety measures will be summarized descriptively using the safety analysis set. Continuous variables will be presented with descriptive statistics (n, mean, standard deviation [SD], median, min, max), within treatment group. Categorical variables will be summarized by treatment group in frequency tables (number of patients and percentage). The denominators for all percentages will be defined as the number of non-missing values for each variable within the analysis set. Percentages will be presented with 1 decimal place.

Primary efficacy variables

- **B-PEth**

One of the primary outcomes will be level of PEth measured in blood.

The primary efficacy variable, B-PEth, is calculated as the mean value over the 8-week steady state active treatment period visit 4 – visit 8 (Day21-Day77) compared to baseline. The data is analyzed as the within patient difference. Day78-Day91 is omitted in the analysis period due to the tendency of drop-out and non-compliance at the end of a study period. Day 0-Day21 is omitted in the analysis due to titration of IMP and optimal timeframe of B-PEth analysis.

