Additionally, B-PEth-level analysis compared to baseline levels will also be performed for Day7, Day 21, Day 35, Day 49, Day 63 and Day 77. B-PEth has a well-documented declining pattern and hence it follows that the mean value during the treatment period will be a sufficient statistic for the post-treatment level. B-PEth will be collected initially at the screening visit and onwards from randomization visit every 2nd week during the study (except for the first visit, which is one week after randomization). An analysis with regards to B-PEth, will be performed using an analysis of covariance (ANCOVA) using the mean value of B-PEth (day21-day77) within patient, as the dependent variable. Adjustments for following covariates will be performed: treatment group, center, nicotine use (Yes/No) and family history positive, FHP (Yes/No).

The ANCOVA model will have fixed effects for treatment and center and subject, nicotine use and FHP will be entered as random effect.

Baseline B-PEth will be used as a covariate in the analysis.

- **Heavy Drinking Days (HDD)**

The additional main outcome will be alcohol consumption as measured by Heavy Drinking Days (HDD) using the Time Line Follow Back (TLFB) procedure. The number of heavy drinking days HDD by 14 days is defined as a mean over the 8-week steady state active treatment period (Day 21 -Day 77) compared to baseline. A HDD is defined in two ways; as ≥ 60 grams for men and ≥ 40 for women according to EMA's guideline and as ≥ 70 grams for men and ≥ 56 grams for women according to FDA's guideline on the development of medicinal products for the treatment of alcohol dependence. The baseline mean of heavy drinking days by 14 days, is obtained at the screening visit, where the number of heavy drinking days over the last 30 days is registered.

The number of heavy drinking days, "HDD 21-77", is the total number of heavy drinking days divided by 4 (8weeks/2), in order to get a 14 day-period measurement. The maximum total number of days measured is 56 days. Additionally, HDD analysis compared to baseline levels will also be performed for Day7, Day 21, Day 35, Day 49, Day 63 and Day 77 and parts of the 8 week steady state active treatment period.

Adjustment for the covariates treatment group, smoking (Yes/No), family history positive, FHP, (Yes/No) and center will be performed. Baseline alcohol consumption will be used as a covariate in the analysis. The

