ANCOVA model will have fixed effects for treatment and center and subject, nicotine use and FHP will be entered as random effect.

Definition of analysis sets

Three analysis sets will be used: Modified Intention-To-Treat (mITT), Per Protocol (PP) and Safety. The primary and secondary efficacy endpoints will be estimated using ITT and PP analysis sets separately. The safety endpoints will be analyzed on the safety analysis set.

1) Modified Intention-to-treat (mITT) analysis set

The mITT analysis set will include all trial subjects who complete screening visit and randomization visit and report that they have taken at least one dose of the randomized IMPs. Subjects will be analyzed according to their randomized IMPs.

2) Per-protocol (PP) analysis set

The PP analysis set constitutes all subjects from the ITT population who are considered to be completers. A completer is defined as a subject who:

- has taken the IMP at least 80% of the planned number of days of the active treatment period
- fulfill the visit milestones, where the visit milestones are met by subjects who have:
 - taken part and completed screening visit, Day 0, Day 21, Day 49 and Day 77
 - successful B-PEth analyses at screening visit, Day 0, Day, 21, Day 49 and Day 77
 - completed TLFB data at screening visit, Day 0, Day, 21, Day 49 and Day 77

In case of violation of any of the above-mentioned criteria the subject will not be included in the PP analysis set for the specific outcome variable. Subjects will be analyzed according to their randomized study drug.

3) Safety set

The safety analysis set includes all subjects who report that they have taken at least one dose of randomized study drug, and for whom any post-dose data is available up until Day 77. Patients will be analyzed according to the actual treatment.

Compliance

Adherence to the study drug regimen will be analyzed by pill count and by plasma levels of IMP1 and IMP2 at visit 4 and visit 6.

Randomization issues

Mistakenly randomizing a subject who does not meet the inclusion/exclusion criteria will be considered a protocol violation. Any such subject will not be included in the analysis sets.

Handling of missing data

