Handling of missing data in the alcohol consumption data as measured by TLFB. In a blind data review, missing data will be assessed. If found appropriate, since we expect that the missing data are not at random, due to the tendency of alcohol patients to have a drinking pattern, we will handle the missing data not by last observation carried forward (LOCF), but instead by an imputation taking the subjects pattern into account. The missing day will be imputed by the data from the same weekday in the weeks before and after, if possible. To adjust for changes in alcohol consumption over time, the weeks closest to the missing day will have a greater weight than the weeks more distant from the missing day.

If a subject drops out from the study in early treatment, the baseline observation will be carried forward. If the subject drops out late in the treatment period the last observed 7 days will be carried forward, if there are missing days, these will be imputed as described above. This model allows for the probability that a longer treatment period will have a greater impact on the alcohol consumption. For all other variables missing data will be considered missing and no imputation will be computed.

All statistical concerns and estimations are described in a separate statistical protocol, the Statistical Analysis Plan (SAP).

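### A falling B-PEth does not make the Day 21–77 mean a sufficient statistic: with missed visits, the primary outcome depends on which visits were observed

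*Protocol*

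**What the plan says.** All of the following is in Protocol section 8.2 unless another section is named.

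- The B-PEth primary variable "is calculated as the mean value over the 8-week steady state active treatment period visit 4" to visit 8, that is Days 21, 35, 49, 63 and 77. It is compared with baseline.
- The model is an ANCOVA "using the mean value of B-PEth (day21-day77) within patient, as the dependent variable", with baseline B-PEth as covariate and terms for treatment, centre, nicotine use and family history.
- The reason given for using the mean is that B-PEth has a "declining pattern and hence it follows that the mean value during the treatment period will be a sufficient statistic for the post-treatment level".
- Under the handling of missing data, drop-out rules are given for the TLFB diary only. Then: "For all other variables missing data will be considered missing and no imputation will be computed".
- The mITT set takes subjects who complete the screening and randomization visits and "report that they have taken at least one dose of the randomized IMPs". It does not require any Day 21–77 B-PEth value.
- The per-protocol set does require "successful B-PEth analyses at screening visit, Day 0, Day, 21, Day 49 and Day 77".
- Section 3.4 adds: "The half-life of PEth is approx. one week".

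**The concern.** Sufficiency is a claim that nothing is lost by replacing the visit values with their mean. A time trend undermines that claim. With a flat level, any subset of visits estimates the same quantity. With a falling level, a mean over the first visits estimates something different from a mean over all five.

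This matters because the mean is the single primary outcome and the protocol rules out imputing B-PEth. A subject seen only on Day 21 would carry the same weight as one seen five times, although the two values refer to different parts of the window and differ in precision. If more subjects leave one arm, or if the arms decline at different rates, the difference in means mixes the treatment effect with the pattern of attendance.

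The point concerns subjects with some Day 21–77 data. Those with none have no outcome under this analysis.

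**Working it through.** **Yardstick.** Section 8.1 gives SD 0.8, 80 per arm, α = 0.025, power 0.80 and a detectable effect of 0.35 µmol/L. With one-sided 0.025 (equivalent to two-sided 0.05), (1.960 + 0.842) × 0.8 × √(2/80) = 0.354 µmol/L, d = 0.443. This reproduces the stated 0.35 and 0.44. The figure serves only as a scale here and does not depend on the point at issue.

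**Inputs the protocol does not give.** The fall in B-PEth within Day 21–77, drop-out by arm within the window, and the within-subject correlation are all assumptions below.

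**1. One leaver, linear fall D from Day 21 to Day 77, continuing after the subject leaves.** Visit levels are 0, −D/4, −D/2, −3D/4 and −D, so the five-visit mean is −D/2.

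| Last visit | Mean of visits seen | Excess over five-visit mean |
|---|---|---|
| Day 21 | 0 | 0.500D |
| Day 35 | −0.125D | 0.375D |
| Day 49 | −0.250D | 0.250D |
| Day 63 | −0.375D | 0.125D |

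If leavers stop evenly over these four visits, the average excess is 1.25D/4 = 0.3125D.

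**2. Arm contrast with no drug effect and equal slopes.** Spurious difference = (drop-out gap) × (average excess).

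- 25% vs 10%, even exits: 0.15 × 0.3125D = 0.047D, which is 0.009, 0.019 and 0.028 µmol/L for D = 0.2, 0.4 and 0.6.
- 35% vs 15%, even exits: 0.20 × 0.3125D = 0.0625D, which is 0.013, 0.025 and 0.038.
- All leavers seen on Day 21 only: from 0.15 × 0.5 × 0.2 = 0.015 to 0.20 × 0.5 × 0.6 = 0.06.

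The range is about 0.01–0.06 µmol/L. Against 0.35 this is 0.009/0.35 = 3% to 0.06/0.35 = 17%. With equal drop-out and equal slopes the difference is zero.

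**3. Equal drop-out but unequal slopes.** Assume only the active arm falls, with D = 0.5. A leaving rate of 5% per visit in both arms shrinks the contrast by 0.03, and 15% per visit shrinks it by 0.08 (9–23% of 0.35).

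**4. Pure washout at the documented half-life.** After a step drop at Day 0, the share still to fall is 0.5^(day/7): 0.125, 0.031, 0.008, 0.002 and 0.0005 at the five visits, mean 0.033. A leaver's excess is 9.2%, 4.5%, 2.1% or 0.8% of the total drop for a last visit on Day 21, 35, 49 or 63. With a total drop of 0.6 µmol/L and a drop-out gap of 15–20 points:

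- all leaving after Day 21: 0.15 × 0.092 × 0.6 = 0.008 to 0.20 × 0.092 × 0.6 = 0.011;
- even exits (average excess 4.15%): 0.004 to 0.005.

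**5. Relapse after leaving.** Take a total drop of 0.5, with 87.5% of it reached by Day 21, then a return to baseline at the remaining visits. The observed value is −0.5 × 0.875 = −0.44. The true five-visit mean is −0.44/5 = −0.09. The observed mean is 0.35 µmol/L too low for that subject, so the sign is the reverse of step 1.

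**6. Precision.** With equal correlation ρ, a k-visit mean has relative variance (1 + (k−1)ρ)/k. At ρ = 0.7 this is 1.00 for one visit and 0.76 for five, a ratio of 1.3.

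**The case against.** The strongest reply is that the endpoint is the period mean, not the last level. A baseline-adjusted ANCOVA on a post-treatment mean is a standard summary-measure analysis, and a mean lying D/2 above the final level is not an error in that endpoint. This stands. The issue is incomplete windows, not the choice of an average.

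Next, the protocol does not literally say that the mean is taken over the visits attended. The text also allows a subject with a gap to count as missing, and section 8.2 refers statistical detail to a SAP that is not at hand. This stands as a caution. On the second reading, however, the subject is lost altogether, and the sufficiency argument is a statement in the protocol itself rather than a detail left for later.

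Third, a one-week half-life means most of a step drop is over by Day 21. True, and the washout part is then small. But in that case there is little decline in the window, so the premise offered for sufficiency goes too.

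Fourth, there are protections: separate analyses at each visit, a per-protocol set needing Days 21, 49 and 77, and an End-of-Treatment sample on discontinuation (sections 3.3 and 4.4). They reduce the problem. They do not correct the mITT primary analysis, and one extra sample does not supply the later visits.

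Two stronger readings are tempting. A reader might infer that leavers' means are always too high. That holds only if the level would have kept falling, and relapse reverses it. A reader might also cite "we expect that the missing data are not at random" as the protocol's own view of missing B-PEth. That remark is made about TLFB data only.

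**Conclusion.** The concern holds in limited form. The sufficiency argument is a non sequitur, and on the natural reading the primary outcome for a leaver depends on which visits were observed while being treated as equivalent to a full five-visit mean.

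The documents do not show that the arm contrast is biased, or in which direction. Bias requires drop-out or slopes to differ between arms, and the protocol states neither. Under the assumed equal linear falls and unequal drop-out, the size is about 0.01–0.06 µmol/L (3–17% of 0.35). It is about 0.01 or less for pure washout and zero when drop-out and slopes are equal. This is a modest effect that can be avoided cheaply. It is worth correcting, but it does not invalidate the design or its power figures.

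**What to change.** - Delete the sufficiency sentence from section 8.2.
- Make the primary B-PEth analysis a repeated-measures mixed model on Days 21, 35, 49, 63 and 77, with treatment, visit, treatment-by-visit, baseline B-PEth-by-visit and the planned covariates (centre, nicotine use, family history), and an unstructured covariance.
- Define the primary contrast as the treatment difference averaged equally over the five visits. This keeps the Day 21–77 average as the target. It also suits the random subject effect that section 8.2 already lists, which needs repeated values per subject.
- Keep the ANCOVA on the within-patient mean as a sensitivity analysis, and state how that mean is formed when visits are missing.
- Add a not-at-random sensitivity analysis, for example one in which leavers return toward baseline.

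The cost is protocol wording and SAS code, with no new data. The drawback is that the primary model assumes missing at random given the observed values. It would not by itself repair the relapse case, which is why the last item is needed. Subjects with no Day 21–77 sample still contribute no outcome.

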(Spanagel and Holter, 2000). Both drugs have been found effective and safe across various populations and are recommended in patients with psychiatric or addictive comorbidity (Aubin et al., 2011) despite their interaction with DA mechanisms.

[figure not shown]

Figure 1. Effects of VAR and BUP alone and in combination on DA levels in rat nucleus accumbens (A), and effect of the combination on the alcohol deprivation effect (B). The BUP doses 2.5, 5.0 and 10.0 indicate mg drug/kg rat weight administered i.p., and the dose of VAR was 1.5 mg/kg.

The evidence of the importance of combating both alcohol and nicotine intake in co-abusers. Nicotine use, mainly in the form of smoking, is significantly more common among individuals with AUDs (Bien and Burge, 1990), and the severity of nicotine dependence is associated with higher craving in alcohol dependent patients (Hillemacher et al., 2006). This co-abuse imposes severe health problems. There is animal evidence indicating that nicotine administration as such by a pharmacological action increases alcohol intake (Blomqvist et al., 1996) (Potthoff et al., 1983) (Smith and Kieval, 2000). Therefore treatment effects on nicotine intake could potentially reduce also alcohol consumption (Prochaska et al., 2004). Also for this reason it is of considerable interest to explore the impact of smoking cessation treatments on alcohol consumption in individuals with AUD, as well as whether the expected effect is related or unrelated to the reduction of nicotine intake.

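### Both primary ANCOVAs carry a subject effect on one value per patient and treat two Yes/No adjustment covariates as random; separately, mITT patients without a B-PEth sample from the Visit 4 window on drop out of the Day 21-77 B-PEth analysis

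*Protocol*

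**What the plan says.** **Outcome.** In Protocol section 8.2 the B-PEth ANCOVA is run "using the mean value of B-PEth (day21-day77) within patient, as the dependent variable". Slightly earlier the same section says: "The data is analyzed as the within patient difference". The HDD variable for Day 21-77 "is the total number of heavy drinking days divided by 4 (8weeks/2), in order to get a 14 day-period measurement". All of these give one number per patient.

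**Covariates.** For B-PEth: "Adjustments for following covariates will be performed: treatment group, center, nicotine use (Yes/No) and family history positive, FHP (Yes/No"). For HDD: "Adjustment for the covariates treatment group, smoking (Yes/No), family history positive, FHP, (Yes/No) and center will be performed". Baseline B-PEth is a further covariate for the first endpoint and baseline alcohol consumption for the second.

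**Model.** For B-PEth: "The ANCOVA model will have fixed effects for treatment and center and subject, nicotine use and FHP will be entered as random effect". The sentence is repeated for HDD: "ANCOVA model will have fixed effects for treatment and center and subject, nicotine use and FHP will be entered as random effect".

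**Who is analysed.** Under the analysis-set definitions in 8.2, mITT membership needs the screening visit, the randomization visit and one reported dose. The B-PEth window runs from Visit 4 to Visit 8. The per-protocol set needs a successful B-PEth result at Day 21, among other visits. Under the missing-data heading, TLFB gaps go to a blind review and may be imputed. Early drop-outs then keep their baseline value, and late drop-outs keep their last observed week. Every other variable, and so B-PEth, is left missing.

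**The concern.** A subject effect belongs in a model with several records per patient. Here the repeated B-PEth samples and the daily drinking records are collapsed to one value before the model is fitted, so the stated model and the stated dependent variable do not fit together. Someone will have to choose what to run instead, for both primary endpoints.

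The second contradiction is inside the covariate specification. The plan says adjustment for nicotine use and FHP will take place, but a random effect is shrunk, and it vanishes when its variance is estimated at zero. With two levels that variance rests on a single contrast, so the trial data would decide whether a promised adjustment happens.

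The third matter concerns patients, not model terms. The two primary endpoints treat someone who leaves early in different ways. Section 1.2 lists showing B-PEth to be superior to self-report as an expected benefit, and section 3.2 says the marker is used to assess PEth as an endpoint measure. A comparison of the two endpoints is harder to read if they rest on different patients and different drop-out rules.

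**Working it through.** **Inputs.** From section 8.1: SD 0.8 µmol/L and 80 per arm for B-PEth; SD 0.35 and 90 per arm for HDD; 360 patients in mITT; alpha 0.025; power 0.80. Assumed, because the protocol gives no figure: the prevalence of nicotine use and FHP (50/50, and 30/70 as a check) and their effects on the outcome (0 to 0.3 SD).

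**1. The plan's own yardsticks.** Detectable difference = SD × √(2/n) × (1.960 + 0.842).
- B-PEth: 0.8 × √(2/80) × 2.802 = 0.354 µmol/L, d = 0.44 (stated 0.35 and 0.44).
- HDD: 0.35 × √(2/90) × 2.802 = 0.146 (stated 15%); 0.15/0.35 = 0.43 as stated.

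Both figures are reproduced when alpha 0.025 is read as one-sided.

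**2. Subject as random.** With one value per patient, Var(y) = σ²(subject) + σ²(residual). Only the sum enters the likelihood. Simulated data (4 arms of 90, 4 centers, baseline covariate) were fitted with the subject share of the variance set at 0, 25, 50, 75 and 100%:

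| Endpoint | REML criterion | Treatment estimate | SE |
|---|---|---|---|
| B-PEth (SD 0.8) | 216.5313 | -0.2493 | 0.1197 |
| HDD as a proportion (SD 0.35) | -270.1664 | -0.1216 | 0.0524 |

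Each row is identical at all five splits. Using the mean or the within-patient difference gives the same figures, because baseline is in the model.

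**3. Subject as fixed.** The sentence can also be read this way. The design then has 8 columns (intercept, 3 treatment, 3 center, baseline) plus 360 subject indicators, 368 in all. Its rank is 360, so residual df = 360 - 360 = 0.

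**4. Two-level random covariates.** The REML variance of a two-level effect is zero when the corresponding 1-df F statistic is below 1. With covariate effect δ (in SD) and split p, the noncentrality is N·p(1-p)·δ². For example, N=360, p=0.5, δ=0.1 gives 360 × 0.25 × 0.01 = 0.9, and P(F<1) = 0.49.

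| Effect (SD) | N=360, 50/50 | N=360, 30/70 | N=320, 50/50 |
|---|---|---|---|
| 0 | 68% | 68% | 68% |
| 0.1 | 49% | 52% | 51% |
| 0.2 | 18% | 23% | 21% |
| 0.3 | 3% | 5% | 5% |

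In 1,000 simulated trials per effect size (N=360, 50/50), at least one of the two adjustments vanished in 88%, 76%, 37% and 7%.

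**5. What this does to the contrast.** A covariate whose variance is set to zero has a fixed-effect coefficient smaller than its SE, about 2 × 0.8/√360 = 0.084 µmol/L. A typical chance imbalance between two arms of 90 is √(2 × 0.25/90) = 0.075. The typical shift for one covariate is therefore below 0.084 × 0.075 = 0.006 µmol/L. The simulations agree:
- B-PEth: mean absolute change 0.003 to 0.004 µmol/L; largest 0.025 in 4,000 trials (0.025/0.35 = 7% of the detectable effect). A two-sided 5% verdict differed in 0.5 to 1.1% of trials.
- HDD (0.1 SD): mean 0.2 and largest 1.0 percentage points, against 15.
- Losing a 0.3 SD covariate entirely multiplies the SE by √(1 + 0.09/4) = 1.011.

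**6. Patients without a Day 21-77 B-PEth value.**
- Section 3.3 allows Visit 4 within 3 days of Day 21, so Day 18 to 24.
- Sections 3.3 and 4.4 require an End-of-Treatment visit on leaving, and that visit includes B-PEth. A sample taken on Day 18-24 might count as Visit 4; the protocol does not say. An earlier one lies outside the window.
- A patient with no sample from about Day 18 on therefore stays in mITT without a dependent variable. The same patient fails the per-protocol Day 21 requirement and appears at most in the additional Day 7 comparison.
- Power is not the main issue. B-PEth was sized on 320 and mITT is planned at 360, so 360 - 320 = 40 patients (11%) can lack the value before the planned number is missed. The early-leaver rate is not given. Over an assumed 2 to 20% of mITT (7 to 72 patients), power for 0.35 µmol/L runs from 0.828 to 0.747, against 0.835 with all 90 per arm.
- Comparability, as an illustration: if a share p leaves early in every arm and baseline is carried forward, those patients contribute zero change, and the HDD difference in mean change is (1 - p) times that among the others. At an assumed 5 to 10%, that is 5 to 10% smaller. B-PEth has no such component.

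**The case against.** The strongest reply is that the model error does almost no harm. Dropping the subject term changes neither estimate nor SE, and random against fixed covariates is a matter of thousandths of a µmol/L. The 68% zero-variance rate applies when the covariate has no effect, so nothing is lost there. All of this stands. A reader might infer that the primary result would be materially distorted; the figures do not support that.

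A reader might also take smoking and nicotine use in the HDD text as two different variables, since section 1.1 says: "Nicotine use, mainly in the form of smoking, is significantly more common among individuals with AUDs". But the HDD model sentence itself says nicotine use, and Table 1 schedules nicotine history, nicotine quantity-frequency and cotinine with no separate smoking measure. This is a slip of terminology.

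On early leavers, three replies carry weight. The End-of-Treatment sample narrows the group affected. The protocol does not define when drop-out counts as early, and TLFB imputation is conditional on the blind review, so the contrast with HDD holds only if the rule covers these patients. And different missing-data rules for a daily calendar and a biweekly blood sample are not in themselves a contradiction. The separate SAP, which is not at hand, may also contain sensitivity analyses, so their absence from the protocol is not the criticism. What remains is what the protocol does fix: no imputation for B-PEth, and an analysis window and per-protocol rule that both exclude the same patients.

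**Conclusion.** The stated primary model is wrong as written for both endpoints. A subject effect on one value per patient is confounded with the residual or exhausts the degrees of freedom, and two promised adjustments are specified so that the data can remove them. The zero-variance rates rest on the assumed splits and covariate effects. The effect on the treatment contrast is small on every assumption tried. The case for correction is that the primary analysis should be fixed in advance and be capable of being run as stated, not that a large shift is expected.

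The early-leaver point also holds, for mITT patients with no B-PEth sample from about Day 18 on. A reader might infer that B-PEth is biased in a known direction, or that the trial becomes underpowered. Neither follows: the number of such patients, their distribution by arm and their later drinking cannot be derived from the document, and the B-PEth sample size has a margin of 40 patients.

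**What to change.** - Delete the subject effect from both ANCOVAs.
- Enter treatment, center, nicotine use and FHP as fixed effects. Keep the baseline covariate already stated for each endpoint: baseline B-PEth, and baseline alcohol consumption for HDD.
- Use the term nicotine use in both covariate lists.
- Keep the Day 21-77 ANCOVA as primary. Report by arm the number of mITT patients without a Day 21-77 B-PEth value.
- Add one B-PEth sensitivity analysis that includes those patients, either with baseline carried forward as for HDD or with delta-adjusted imputation.

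The cost is wording in section 8.2 and the SAP before unblinding, standard code, one count and one extra analysis. No new data are needed and the sample size is unchanged, since it rests on a t-test. The downside is that the added analysis depends on an assumption about early leavers that the data cannot test.
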